8.1.7 Injection site reactions

Injection site reactions will use an investigator-driven definition, i.e. will be directly determined from what is entered on the eCRF.

A subject will be considered to have this AESI if the subject has at least one preferred term with AE onset date during the relevant study period for analysis, which has "AE category" on the Adverse Events eCRF page marked as "Injection Site Reaction".

8.1.8 Opportunistic infections

Opportunistic infections will be defined using a pre-specified list of preferred terms (AZ defined SMQ).

8.1.9 Guillain-Barre syndrome

Guillain-Barre syndrome will be defined using an SMQ: Guillain-Barre (narrow).

8.1.10 Adrenal crisis (D5180C00009 only)

Adrenal crisis will be defined using a pre-specified list of high level and lower level MedDRA terms.

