## 2.1 Study rationale

There are two Phase 3 studies currently ongoing.

The Navigator study (D5180C00007) is designed to evaluate the effect of tezepelumab on the AAER, lung function, asthma control, and safety in adult and adolescent subjects with uncontrolled severe asthma receiving medium or high-dose ICS plus at least one additional asthma controller medication with or without OCS. This will allow the benefit-risk profile of tezepelumab in the treatment of severe asthma to be further characterized and to enable a better understanding of how treatment with tezepelumab should be utilized in the management of severe asthma.

The Source study (D5180C00009) is designed to demonstrate the ability of tezepelumab versus placebo to enable reductions of the daily maintenance OCS use in adult asthmatic subjects who are also using high-dose ICS plus LABA with or without other asthma controller therapy, while maintaining asthma control.

Tezepelumab is a fully humanized immunoglobulin that binds to the TSLP and prevents its interaction with the TSLP receptor. TSLP has an upstream and central role in the initiation of the immune responses and is expected to have an impact on a broad range of cell types. In the predecessor studies the safety of tezepelumab dosing is being studied over a 52 week and 48 week treatment period in the D5180C00007 and D5180C00009 studies respectively. However, it is important to further understand the safety with continued dosing of tezepelumab for an additional year. The purpose of this Long-Term Extension (LTE) study is to continue to characterize the safety profile of tezepelumab administration in asthma subjects who have completed either of the 2 predecessor studies. CC

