## **6.5 Concomitant therapy**

All subjects will be taking medium- or high-dose ICS and potentially at least one additional asthma controller medication (including LABA, Leukotriene modifiers, theophylline, cromones). Additionally, the subject may be taking OCS for the treatment of asthma.

During the study, subjects may use an inhaled short-acting bronchodilator as needed as a reliever or rescue medication due to worsening of asthma.

Maintenance regimen of allergen-specific immunotherapy is allowed but should not be administered on the same day as investigational product.

Tezepelumab - D5180C00018

Investigators may prescribe concomitant medications or treatments to provide adequate supportive care as deemed necessary, except for those medications identified as “excluded” in Prohibited medications. See [Table 7](#).

Maintenance asthma medication is not regarded as an IP but will be provided/reimbursed by AstraZeneca according to local regulations in order to maintain appropriate oversight and access to this concomitant therapy. Any marketed (e.g. omalizumab, mepolizumab, reslizumab, etc.) or to be marketed or investigational biologic treatment will not be provided/reimbursed by AstraZeneca.

Any medication or vaccine including over-the-counter or prescription medicines, vitamins, and/or herbal supplements that the subject is receiving at the time of enrolment or receives during the study must be recorded along with:

- Reason for use
- Dates of administration including start and end dates

All concomitant medication should be documented in the source and recorded in the eCRF.

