### **8.3.8 Adverse Events of Special Interest**

An adverse event of special interest (AESI) is an event of scientific and medical interest towards improving the understanding of the IP. An AESI may be serious or non-serious. For this study, AESIs include:

1. Anaphylactic reactions
2. Immune complex disease (Type III hypersensitivity reactions)
3. Malignancy
4. Helminth infections
5. Severe infections which are defined as:

Tezepelumab - D5180C00018

- SAEs or
  - Requiring treatment with systemic antiviral medications, intravenous antibiotics or medications for helminth parasitic infection or
  - Requiring a premature and permanent discontinuation of study drug
6. Injection site reactions
  7. Opportunistic infections
  8. Guillain-Barre Syndrome
  9. Adrenal crisis

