#### 9.4.2 Safety analyses

All safety analyses will be performed on the safety analysis set. Key safety analyses will be repeated using the SAF-LTE analysis set.

The primary objective of the study to evaluate the long-term safety and tolerability of tezepelumab in severe asthma subjects will be assessed through on-treatment AEs (including AESIs, as defined in Section 8.3.8) and SAEs. AEs, AESIs and SAEs will be summarized using exposure adjusted incidence rates (i.e., number of subjects reporting events divided by person-time at risk) to account for the variability in follow-up. CCI

The definition of on-treatment AEs and post-treatment AEs will be defined in the SAP.

The treatment groups for addressing the primary objective will be “Randomized Tezepelumab” and “Randomized Placebo” using the safety analysis set. Supportive analysis of key safety data will be presented for the “Tezepelumab Predecessor+Tezepelumab LTE” and “Placebo Predecessor+Placebo LTE” treatment groups using the SAF-LTE analysis set. Summaries for these 4 treatment groups will be provided overall (Week 0 to Week 104) and by time period

Tezepelumab - D5180C00018

(Week 0 to Week 52/48, Week 52/48 to Week 104). An additional summary of key safety data will be provided for the “Placebo Predecessor+Tezepelumab LTE” treatment group for the SAF-LTE analysis set by time period (Week 0 to Week 52/48, Week 52/48 to Week 104) only.

CCI The “All Tezepelumab” treatment group may additionally be used to report AESIs (rare events) for the safety analysis set. In addition, AESIs may be assessed using the pooled data across the 2 studies.

Laboratory data will be summarized by presenting shift tables using normal ranges (baseline in predecessor study to most extreme post-baseline value) and by presenting summary statistics of observed and change from baseline values (means, medians, quartiles, ranges). The incidence of clinically notable laboratory abnormalities will be summarized.

Further details on additional analyses and presentation of safety data will be provided in the SAP.

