4.3 Prior and concomitant medications

Unless stated otherwise, for all the summaries described in this section, summaries using the SAF analysis set will present the Randomised Tezepelumab and Randomised Placebo treatment groups; summaries using the SAF-LTE analysis set will present the Tezepelumab Predecessor+Tezepelumab LTE and Placebo Predecessor+Placebo LTE treatment groups. In addition, any summaries split by predecessor period and LTE period for the SAF-LTE analysis set will also include the Placebo Predecessor+Tezepelumab LTE treatment group.

The number and percentage of subjects receiving each medication (by ATC classification system codes and generic name) will be presented by treatment for the SAF and SAF-LTE analysis sets. Separate tables will be presented for all medications received during each of the following periods as defined in Section 3.1.7: Prior, Concomitant (on-treatment), Concomitant (post-treatment) for the SAF and SAF-LTE analysis sets. Summaries of Concomitant (on-treatment) medications during the predecessor period and LTE period will also be provided by the SAF and SAF-LTE analysis sets. Summaries of Prior and Concomitant (post-treatment) for the SAF-LTE analysis set will also include the Placebo Predecessor+Tezepelumab LTE treatment group.

Tables for maintenance medications (started prior to and ongoing after the first day of IP) will be produced displaying the baseline total daily dose categories (low/medium/high) of ICS medications for the SAF and SAF-LTE analysis sets. The number of subjects using other maintenance asthma medications at baseline will also be summarised for the SAF and SAF-LTE analysis sets.

In addition, the total number of days of systemic corticosteroid treatment associated with asthma exacerbations per subject from the first day of IP up to Week 104 will also be summarised for the SAF and SAF-LTE, and also split by predecessor and LTE periods.

For study D5180C00007, summary statistics will be produced of total daily OCS dose converted to a prednisone equivalent irrespective of reason/condition treated (for subjects taking OCS at baseline). Conversion factors to be applied for this purpose are given in Appendix 8.2.

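### SAP 8.1.10 limits the adrenal crisis AESI to D5180C00009, although the protocol lists it for the whole study; the restriction is neither explained nor declared

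*SAP*

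**What the plan says.** - **Protocol 8.3.8** introduces its list with "For this study, AESIs include". Item 9 is "Adrenal crisis". No item is tied to a predecessor study.
- **Protocol 9.4.2** says the primary objective will be assessed through "on-treatment AEs (including AESIs, as defined in Section 8.3.8) and SAEs". It also allows AESIs to be reported for the All Tezepelumab group and on data pooled across the two studies.
- **SAP 3.2.3** leaves it to the protocol to specify the AESIs and sends the reader to Appendix 8.1 for how each is derived.
- **SAP Appendix 8** then has, at 8.1.10, the heading "Adrenal crisis (D5180C00009 only", with the bracket closed after it. The text below defines the category by a pre-specified list of MedDRA terms at the high and lower levels. It gives no reason for the restriction.
- **SAP Table 10** labels three AESI rows as applying to *Both* studies: category by SOC/PT, category by PT and causality, and exposure adjusted occurrence rate.
- **SAP Section 1** says departures from the protocol will be described in Section 6. **SAP Section 6** lists only the new LTE analysis set.
- **OCS use in D5180C00007.** Protocol 2.1 describes that study's subjects as "receiving medium or high-dose ICS plus at least one additional asthma controller medication with or without OCS". Protocol 6.5 says of all subjects in the extension: "Additionally, the subject may be taking OCS for the treatment of asthma". SAP 4.3 states: "For study D5180C00007, summary statistics will be produced of total daily OCS dose converted to a prednisone equivalent".

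**The concern.** The SAP narrows a category that the protocol sets for the whole study and ties to the primary objective. It does so in an appendix heading, without a rationale and without the declaration that its own Section 1 promises. The excluded predecessor study is by far the larger one, and the SAP itself expects some of its subjects to be on OCS.

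The stake is the grouped view of a rare event. AESI summaries gather scattered terms into one count of subjects and one rate per arm. If the category is built in one study only, a reader of the D5180C00007 results cannot tell from the AESI tables whether there were no cases or whether the category was never derived.

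**Working it through.** **1. Do the passages agree?**

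| Source | Scope of the adrenal crisis AESI |
|---|---|
| Protocol 8.3.8 | Whole study |
| Protocol 9.4.2 | Whatever 8.3.8 defines; pooling across studies allowed |
| SAP 3.2.3 | As specified by the protocol |
| SAP Table 10 | *Both*, for a generic row covering each AESI category |
| SAP 8.1.10 | D5180C00009 only |
| SAP Section 6 | No change declared |

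SAP 8.1.10 stands alone. The label *Both* in Table 10 carries information, because the same table marks single-study rows as such: total daily OCS dose is marked C00007, and the two rows on OCS at entry and optimised dose are marked C00009.

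**2. How many subjects fall outside the category?**

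Inputs, from Protocol 9.2 and SAP 1.3: 860 subjects expected from D5180C00007 and 115 from D5180C00009; 90% complete the predecessor study and 90% of those roll over.

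- The plan's own total: 860 + 115 = 975. It reproduces.
- Share outside: 860 / 975 = 88.2%. Share covered: 115 / 975 = 11.8%.
- The primary safety set includes all dosed predecessor subjects, whether or not they roll over. Completion times roll-over is 0.90 × 0.90 = 0.81. Dividing gives 860 / 0.81 ≈ 1,062 and 115 / 0.81 ≈ 142, about 1,204 in all. The share outside is again 88.2%, because both studies are scaled by the same factor.
- Sensitivity: let the combined completion and roll-over rate be *a* in D5180C00007 and *b* in D5180C00009, each between 0.70 and 0.90 (my assumption). The share outside is 1,062*a* / (1,062*a* + 142*b*).
  - *a* = 0.70, *b* = 0.90: 743 / (743 + 128) = 85%.
  - *a* = 0.90, *b* = 0.70: 956 / (956 + 99) = 91%.

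**3. What is lost for D5180C00007, and what is kept?**

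| Output (SAP 4.5.1, Table 10) | D5180C00007 under 8.1.10 as written |
|---|---|
| Grouped AESI incidence rate by arm | Lost |
| Grouped AESI causality table | Lost |
| AESI exposure adjusted occurrence rate | Lost |
| Contribution to an All Tezepelumab or pooled summary of this AESI | Lost |
| All AEs and SAEs by SOC/PT, with incidence rate per 100 subject-years by arm | Kept |
| AEs by PT with causality and with maximum intensity | Kept |
| AE listing (SAF-LTE) | Kept |

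The kept rows do not in general add up to the lost one. Under SAP 3.2.2 the incidence rate counts subjects, so a subject with two different listed terms appears in two PT rows but once in the grouped category. The list is also set at MedDRA levels other than the preferred term, so it need not match whole PT rows. How far the two differ cannot be worked out here, because the list is not reproduced in the SAP.

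**The case against.** The strongest reply is that little is hidden. A reader might infer that D5180C00007 would have no adrenal crisis rate in either arm. The documents do not support that: a coded event there gets a PT-level incidence rate by arm and a causality row, and PT-level All Tezepelumab tables are planned too. SAP 8.1.2 accepts general SOC/PT reporting instead of separate tables for another protocol AESI, immune complex disease. That precedent has limits. It covers an AESI defined by a single preferred term, and the SAP says openly that no separate table is needed. Neither is true of adrenal crisis.

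A second reply is that Table 10's row is generic and can be read together with a restriction in the appendix. That is possible, and it makes Table 10 supporting evidence only. The conflict with Protocol 8.3.8 and 9.4.2 and the silence of Section 6 do not depend on it.

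A third reply is that D5180C00009 is the study designed around reducing maintenance OCS, so a reason can be guessed. It can, but the SAP does not state one. The SAP also expects OCS users in D5180C00007: it summarises their dose in 4.3 and defines an OCS present/absent subgroup in 3.1.8.

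A reader might also argue that inhaled corticosteroid dose or stepping down background medication puts D5180C00007 subjects at risk of adrenal crisis. Nothing in the documents says so, and the point does not rely on it.

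**Conclusion.** The mismatch is real and undeclared. One protocol-specified AESI loses its grouped summaries for the predecessor study that supplies 860 of the 975 planned extension subjects, or 88% (85% to 91% if completion and roll-over differ between studies within the assumed range).

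Three limits apply to that figure:

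- It is based on planned numbers, not on actual enrolment.
- It is a share of all subjects. The documents do not give the number of OCS users in D5180C00007, so the 88% must not be read as the share of subjects at risk who are missed.
- It counts subjects, not exposure. The plan's expected subject-years are blacked out in the public text, and any reconstruction would rest on guessed follow-up, so none is offered.

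The primary outcome measure, incidence rates of AEs and SAEs, is still analysed in full for D5180C00007. What is narrowed is one AESI within the assessment of the primary objective.

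**What to change.** Delete the parenthetical restriction from the heading of SAP 8.1.10. Apply the same pre-specified MedDRA term list to subjects from both predecessor studies and keep reporting the two studies separately, as elsewhere in the SAP. Table 10 then needs no change.

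The cost is one more AESI category in D5180C00007 tables that are already planned, probably with few events. The term list is needed for D5180C00009 in any case, and no new data are collected.

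If the sponsor has a reason to keep the restriction, it should be stated in 8.1.10, declared in Section 6 and marked in Table 10. That would settle the inconsistency but would not restore the grouped summary for D5180C00007, so deletion is the better choice.

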8.2 OCS conversion factors for prednisone equivalents

Total daily OCS dose will be converted to a prednisone equivalent using the following table:

Table 7 Estimated OCS dose therapy equivalence

| Oral Corticosteroid | Approximate equivalence dose |
|---------------------|------------------------------|
| Prednisone | 10 mg |
| Prednisolone | 10 mg |
| Cortisone | 50 mg |
| Hydrocortisone | 40 mg |
| Methylprednisolone | 8 mg |
| Triamcinolone | 8 mg |
| Betamethasone | 1.2 mg |
| Dexamethasone | 1.5 mg |
| Deflazacort | 12 mg |

For example, to convert a cortisone total daily dose to a prednisone equivalent total daily dose, a multiplication factor of 0.2 = 10/50 should be used.

8.3 Maintenance Therapy Equivalence Table

 Table 8
 Estimated daily doses for inhaled corticosteroids

| Asthma Therapy | Total Daily Dose (μg/day) | | | |
|------------------------------------|---------------------------|-----------|-------|--|
| Inhaled Corticosteroid | Low | Medium | High | |
| Beclomethasone dipropionate (CFC)* | 200-500 | >500-1000 | >1000 | |
| Beclomethasone dipropionate (HFA) | 100-200 | >200-400 | >400 | |
| Budesonide (DPI) | 200-400 | >400-800 | >800 | |
| Ciclesonide (HFA) | 80-160 | >160-320 | >320 | |
| Fluticasone furoate (DPI) | 100 | n.a. | 200 | |

| Asthma Therapy | Total Daily Dose (μg/day) | | | | |
|------------------------------|---------------------------|------------|-------|--|--|
| Inhaled Corticosteroid | Low | Medium | High | | |
| Fluticasone propionate (DPI) | 100-250 | >250-500 | >500 | | |
| Fluticasone propionate (HFA) | 100-250 | >250-500 | >500 | | |
| Mometasone furoate | 110-220 | >220-440 | >440 | | |
| Triamcinolone acetonide | 400-1000 | >1000-2000 | >2000 | | |

CFC: Chlorofluorocarbon propellant; DPI: dry powder inhaler; HFA: hydrofluroalkane propellant.

^{*} Included for comparison with older literature. From GINA 2018

8.4 Summary of data to be presented

Table 9 Disposition, demographics and baseline characteristics

| Analysis sets | | SAF | | SAF-I | LTE | LTE | CCI |
|---|--|--------------------------|------------|-------------------------|------------|--------------------------------------|-----|
| | Treatment groups | (Rand Teze/ Rand Pbo) | (All Teze) | (Teze+Teze/ Pbo+Pbo) | (Pbo+Teze) | (Teze+Teze/ Pbo+Pbo/ Pbo+Teze) | |
| Study | Data | Overall | Overall | Overall | Overall | Overall | |
| Disposition, demographics and baseline characteristics (Section 4.2, 4.7.1) | | | | | | | |
| Both | Disposition | √ PreD | | | | ✓ LTE | |
| Both | Demographics | ✓ | ✓ | ✓ | ✓ | | |
| C00007 | Demographics by age group $(\ge 12 \text{ to } < 18, \ge 18 \text{ to } < 65, \ge 65)$ | | | ✓ | ✓ | | |
| Both | Baseline characteristics | ✓ | √ | ✓ | ✓ | | |
| C00007 | Baseline characteristics by age group $(\ge 12 \text{ to } < 18, \ge 18 \text{ to } < 65, \ge 65)$ | | | ✓ | ✓ | | |
| Both | Time to last dose/withdrawal from study | ✓ | | | | | |

 $\sqrt{\text{PreD}}$ = Predecessor period only;

 \sqrt{LTE} = LTE period only;

CC

C00007 = D5180C00007;

Rand Teze = Randomised Tezepelumab;

Rand Pbo = Randomised Placebo;

Teze+Teze = Tezepelumab Predecessor+Tezepelumab LTE;

Pbo+Teze = Placebo Predecessor+ Tezepelumab LTE;

Pbo+Pbo = Placebo Predecessor+Placebo LTE;

All Teze = All Tezepelumab;

Table 10 Important PDs, medications, safety and tolerability, and efficacy

| Analysis sets | | SAF | SAF/FAS | | SAF-LTE/FAS-I | CTE CC | CI |
|---------------|---|--------------------------|------------|---------|--------------------------|-----------------------|----|
| Treatmen | nt groups | (Rand Teze/ Rand Pbo) | (All Teze) | ` | ze+Teze/ o+Pbo) | (Pbo+Teze) | |
| Study | Data | Overall | Overall | Overall | By period (PreD, LTE) | By period (PreD, LTE) | |
| Importa | nt protocol deviations (Section 4.2, 4.7.1) | | | | | | |
| Both | Important PDs | | | | √ | ✓ | |
| Prior an | d concomitant medications (Section 4.3) | | | | | | |
| Both | Prior | ✓ | | ✓ | | √Overall | |
| Both | Concomitant (on-treatment) | ✓ | | ✓ | ✓ | √ | |
| Both | Concomitant (post-treatment) | ✓ | | ✓ | | √Overall | |
| Both | Maintenance medications | ✓ | | ✓ | | | |
| Both | Days of systemic corticosteroids | ✓ | | ✓ | √ | √ | |
| C00007 | Total daily OCS dose | ✓ | | ✓ | √ | √ | |
| C00009 | OCS medication at study entry/baseline | ✓ | | ✓ | | | |
| C00009 | OCS baseline to optimised dose | ✓ | | ✓ | | | |
| Both | Disallowed Medications (prior) | ✓ | | ✓ | | √Overall | |
| Both | Disallowed Medications (on-treatment) | ✓ | | ✓ | √ | √ | |
| Both | Disallowed Medications (post-treatment) | ✓ | | ✓ | | √Overall | |
| Both | Biologics (prior) | ✓ | | ✓ | | √Overall | |
| Both | Biologics (post-treatment) | √ | | ✓ | | ✓ Overall | |
| Exposur | re and compliance (Section 4.4) | | | | | | |

| Analysis | Analysis sets | | //FAS | SAF-LTE/FAS-LTE | | | CCI |
|-------------------------|---|--------------------------|-------------|-----------------|--------------------------|-----------------------|-----|
| Treatme | nt groups | (Rand Teze/ Rand Pbo) | (All Teze) | ` | ze+Teze/ o+Pbo) | (Pbo+Teze) | |
| Study | Data | Overall | Overall | Overall | By period (PreD, LTE) | By period (PreD, LTE) | |
| Both | Exposure | ✓ | √ +C | ✓ | ✓ | ✓ | |
| Both | Compliance | ✓ | | ✓ | ✓ | ✓ | |
| Both | Total number of dosing occasions | ✓ | ✓ | ✓ | | | |
| SAFETY and TOLERABILITY | | | | | | | |
| Adverse | events (Section 4.5.1, 4.7.2) | | | T | | | |
| Both | Overall summary | √+SG | √On-Trt | √ | ✓ | ✓ | |
| Both | AEs by SOC/PT | √+SG | √On-Trt | ✓ | √ | ✓ | |
| Both | AEs by PT and causality | ✓ | | ✓ | ✓ | ✓ | |
| Both | AEs by PT and max intensity | ✓ | | ✓ | ✓ | ✓ | |
| Both | SAEs by SOC/PT | √+SG | √On-Trt | √+SG | √+SG | ✓ | |
| Both | Fatal AEs by SOC/PT | ✓ | | ✓ | ✓ | ✓ | |
| Both | DAEs by SOC/PT | √+SG | √On-Trt | √+SG | √+SG | ✓ | |
| Both | DAEs causally related to IP by SOC/PT | ✓ | | ✓ | ✓ | ✓ | |
| Both | SAEs leading to discontinuation by SOC/PT | ✓ | | ✓ | ✓ | ✓ | |
| Both | Each AESI category by SOC/PT | ✓ | √On-Trt | √ | √ | √ | |
| Both | Each AESI category by PT and causality | ✓ | | ✓ | ✓ | ✓ | |

| Analysis sets | | SAF | SAF/FAS | | SAF-LTE/FAS-I | LTE | CCI |
|--|---|--------------------------|------------|----------|--------------------------|--------------------------|-----|
| Treatme | nt groups | (Rand Teze/ Rand Pbo) | (All Teze) | , | ze+Teze/ o+Pbo) | (Pbo+Teze) | |
| Study | Data | Overall | Overall | Overall | By period (PreD, LTE) | By period (PreD, LTE) | |
| Both | Further summaries of AESI of injection site reactions | ✓ | | √ | ✓ | √ | |
| Both | Most common AEs by PT only | ✓ | | ✓ | ✓ | ✓ | |
| Both | Adjudicated AEs | ✓ | | ✓ | ✓ | ✓ | |
| Both | AESIs - exposure adjusted occurrence rate | ✓ | √On-Trt | ✓ | ✓ | √ | |
| Laboratory data (Section 4.5.2, 4.7.2) | | | | | | | |
| Both | Haematology/Clinical chemistry - summaries over time | √By period (PreD, LTE) | | | | √ | |
| Both | Haematology/Clinical chemistry - shift tables and shift plots | ✓ | | ✓ | | | |
| Both | Hy's law | ✓ | | ✓ | | | |
| Both | Urinalysis - shift tables | ✓ | | ✓ | | | |
| Vital Sig | gns (Section 4.5.3, 4.7.2) | | | | | | |
| Both | Vital signs - summaries over time | √By period (PreD, LTE) | | | ✓ | ✓ | |
| Both | Vital signs - shift tables and shift plots | ✓ | | ✓ | | | |
| ECG (S | ection 4.5.4) | | | | | | |
| Both | ECG - shift tables | ✓ | | ✓ | | | |
| EFFIC | ACY | | | | | | |
| Exacerbations (Section 4.6.1, 4.6.2.5, and 4.7.3.2) | | | | | | | |

| Analysis | sets | SAF/FAS | | SAF-LTE/FAS-LTE | | CCI | |
|----------|-----------|--------------------------|------------|-----------------|--------------------------|--------------------------|--|
| Treatme | nt groups | (Rand Teze/ Rand Pbo) | (All Teze) | (Tez Pbo | e+Teze/ o+Pbo) | (Pbo+Teze) | |
| Study | Data | Overall | Overall | Overall | By period (PreD, LTE) | By period (PreD, LTE) | |
| CCI | | | | | | | |
| | | | | | | | |
| | | | | | | | |
| | | | | | | | |
| | | | | | | | |
| | | | | | | | |
| | | | | | | | |
| | | | | | | | |
| | | | | | | | |
| | | | | | | | |

| Analysis | nalysis sets | | SAF/FAS | | SAF-LTE/FAS-LTE | | CCI |
|----------|--------------|--------------------------|------------|---------|--------------------------|--------------------------|-----|
| Treatme | nt groups | (Rand Teze/ Rand Pbo) | (All Teze) | | e+Teze/ o+Pbo) | (Pbo+Teze) | |
| Study | Data | Overall | Overall | Overall | By period (PreD, LTE) | By period (PreD, LTE) | |
| CCI | | | | | | | |
| | | | | | | | |
| | | | | | | | |
| | | | | | | | |
| | | | | | | | |
| | | | | | | | |
| | | | | | | | |
| | | | | | | | |
| | | | | | | | |

| Treatment groups (Rand Teze/Rand Pbo) (All Teze) (Pbo+Teze) Study Data Overall Overall Overall Overall Overall (PreD, LTE) Overall Overall | Analysis | sets | SAF/FAS | | SAF-LTE/FAS-LTE | | | CCI |
|---|----------|-----------|---------|------------|-----------------|--|------------|-----|
| (PreD, LTE) (PreD, LTE) | Treatmen | nt groups | , | (All Teze) | ` | | (Pbo+Teze) | |
| CCI | Study | Data | Overall | Overall | Overall | | | |
| | CCI | | | | | | | |

⁺C = Also produced for combined data from D5180C00007 and D5180C00009;

FAS and FAS-LTE were only applicable for efficacy analyses; Otherwise, SAF and SAF-LTE were applied;

CC

 $\sqrt{\text{On-Trt}} = \text{On-treatment period only};$

 $\sqrt{\text{LTE}} = \text{LTE period only};$

CC

C00007 = D5180C00007;

C00009 = D5180C00009;

Rand Teze = Randomised Tezepelumab;

Rand Pbo = Randomised Placebo;

Teze+Teze = Tezepelumab Predecessor+Tezepelumab LTE;

Pbo+Teze = Placebo Predecessor+ Tezepelumab LTE;

Pbo+Pbo = Placebo Predecessor+Placebo LTE;

All Teze = All Tezepelumab;

⁺SG = Also produced for subgroups for D5180C00007 only (on-treatment period only for safety data, planned treatment period only for efficacy data);

